9.2 Efficacy Analysis

The proportion of patients with nonulcerative recurrences which do not progress to vesicles (Phase 3) will be compared between treatment groups using a χ^2 test. The episode duration and lesion size parameters will be compared between the treatment groups with a two-sample Student t-test. The time to lesion healing will be assessed using Kaplan-Meier methods. To illustrate the total clinical benefit of EED, an analysis of time to lesion healing and lesion area for all recurrences (i.e., including both ulcerative lesions and nonulcerative recurrences) will be performed as “all lesions.” In this analysis, the impact of prevention of ulcerative lesions will be introduced by assigning zero values to nonulcerative recurrences.

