6.1.4 Study Days 3, 5, and 7 Visits

On Days 3, 5, and 7, the subject will present for a follow up appointment in clinic or via virtual video call consisting of:

- Review of the subject’s diary card to identify possible treatment emergent adverse events.
- Assessment of the subject’s pain on a visual analog scale.
- Measurement of the lesion will be taken (if lesion is present).
- Photographs of area exposed to UV radiation may be asked to be taken by subjects and uploaded into their MyChart account. If patients are present in clinic, photographs will be taken by study staff.
- If the subject has experienced a prodrome or lesion they should have started dosing. The study staff will review their dosing compliance and examine the study product tube/bottle. If the subject is not complying with the dosing regimen, the study staff will determine whether non-compliance is serious enough to warrant terminating the subject’s participation. Otherwise, minor non-compliance should be noted, and the subject should be retrained on how to dose themselves.

Once patients reach the Stage 2/3 lesion their lesion may be swabbed for viral culture (HSV PCR). If the patient reaches Stage 2/3 over the weekend, the lesion will not be swabbed. We will reserve this for the first five patients but may continue to do all patients to ensure lesion is in fact a cold sore and not a reaction to the UV radiation.

6.1.5 EOS – End of Study Visit (Day 10 – or after subject’s lesion has fully healed)

An EOS visit will occur after the subject’s lesion has fully healed or Day 10 (whichever comes first), the subject will present to the clinic for a follow up appointment in clinic or via virtual video call consisting of:

- Review of the subject’s diary card to identify possible treatment emergent adverse events. If the subject has an AE that has not resolved by this time, the site staff will explain to the subject that they will be called every week to check on the status of the AE, until it is resolved.
- Assessment of the subject’s pain on a visual analog scale.

- Photographs of area exposed to UV radiation may be asked to be taken by subjects and uploaded into their MyChart account. If patients are present in clinic, photographs will be taken by study staff.

The subject's diary card and all tubes//bottles of study product (empty, partially used or unused) will be collected and the subject will be released from the study.

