6.2 Early Discontinuation Visit

If at any time during the study, a subject wants to stop participating or the Investigator believes it is in the subject's best interest to stop treatment, every effort should be made to complete the final assessments noted in the EOS visit.

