7. EFFICACY EVALUATIONS

7.1 Number of subjects that experience prodrome (Stage 1) but do not progress to vesicles (Stage 3) by completion of treatment

The Principal Investigator or his designee will review all photographs taken from Day 1 through the EOS visit against the onset of prodrome date and the date of healing or 7 full days of treatment noted on the subject's diary card. They will then determine the duration of the HSV outbreak (prodrome to healed). This may or may not agree with the subject's assessment of "healed" but should be based on the collective information gathered during the subject's time on study. The blinded assessor will assess the prodrome and/or lesion at every clinic visit starting at day 3. The blinded assessor will only be responsible for the rating of the prodrome and or/lesions. The blinded assessor will not be performing safety evaluations. The unblinded staff will instruct the subject to not talk with the blinded assessor about which treatment they have been using.

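### Episode duration is compared by a t-test that has no value for a lesion unhealed at Day 10, while the Kaplan-Meier analysis that could use it has no between-arm contrast

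*Combined protocol and SAP*

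**What the plan says.** **Analysis (Section 9.2).** "The episode duration and lesion size parameters will be compared between the treatment groups with a two-sample Student t-test". Time to lesion healing is to be assessed by Kaplan-Meier. No log-rank test, median difference, restricted mean or censoring date is given. The only rule for assigning a value is zero for nonulcerative recurrences in the all-lesions analysis.

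**Derivation of duration (Section 7.1).** Photographs from Day 1 through EOS are reviewed against the prodrome date and "the date of healing or 7 full days of treatment noted on the" diary card. Then: "They will then determine the duration of the HSV outbreak (prodrome to healed"). The judgement "should be based on the collective information gathered during the" subject's time on study. The section's heading is the primary endpoint, subjects who "do not progress to vesicles (Stage 3) by completion of treatment".

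**Follow-up.** Section 6.1.4: "On Days 3, 5, and 7, the subject will present for a follow up appointment". Section 6.1.5 places EOS once the "lesion has fully healed or Day 10 (whichever comes first"). Section 3 says the same, and that most lesions will have resolved by Day 7. The synopsis (Design and Treatment Period) provides for subjects who reach EOS with lesions not fully resolved.

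**Endpoint definitions.** Section 2.1.2 measures duration until loss of the hard crust. The synopsis (Efficacy Assessments) measures it from Stage 3 to complete healing at Stage 5. Section 7.1 starts it at the prodrome.

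**The concern.** A two-sample t-test has no place for an episode whose healing was not seen. Someone must enter a number (the last day, Day 10, Day 7) or drop the subject, and the plan does not say which. At about 10 per arm, one or two such subjects can move the estimate. The rule could also be chosen after the data are seen, in a study where only the efficacy assessor is blinded. Kaplan-Meier handles these episodes properly, but without a named contrast it yields two curves and no comparison. The 7-day wording in Section 7.1 adds a second candidate end date. At stake are the size and meaning of the duration result; the primary endpoint is not involved.

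**Working it through.** **Inputs.** Recurrent lesions heal in 5 to 10 days (Section 1.1); most resolve by Day 7 (Section 3); follow-up ends at healing or Day 10 (Sections 3 and 6.1.5); 20 completers at 1:1, so about 10 per arm (Sections 4.3 and 5). The documents give no effect size, standard deviation, alpha or power, so there is no planned figure to reproduce. Everything below is illustrative, with a two-sided 5% level assumed.

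**1. Which end date?** Sections 2.1.2 and 7.1 and the synopsis all end duration at healing, and the photographs run to EOS. Only the mention of 7 full days in Section 7.1 points elsewhere, and that section is headed by an endpoint judged at completion of treatment. Healing is the natural end date; the text does not rule out the other.

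**2. Effect of closing at Day 7, assumed uniform healing times.** For X uniform on (a, b) and a cap k between them, E[min(X, k)] = (a+b)/2 − (b−k)²/[2(b−a)].
- Comparator 4–9: 6.5 − 2²/10 = 6.1. EED 3–8: 5.5 − 1²/10 = 5.4. A true difference of 1.0 becomes 0.7. Unhealed at Day 7: 2/5 = 40% v 1/5 = 20%.

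**3. Same question, assumed lognormal times.** The 5 to 10 days are taken as the central 95% or the central 80% range, with medians 1 day apart.

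| Rule | Difference (days) |
|---|---|
| True | 1.01 to 1.04 |
| Followed to Day 10 | 0.94 to 1.00 |
| Closed at Day 7 | 0.51 to 0.58 |
| Unhealed at Day 10 left out | 0.75 to 0.93 |
| Unhealed at Day 7 left out | 0.33 to 0.39 |

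Here 2.5% to 10% of comparator lesions are unhealed at Day 10. About 52% are unhealed at Day 7, which sits uneasily with most having resolved by then.

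**4. A harsher case.** Uniform 5–12 v 4–11 leaves 2/7 = 29% v 1/7 = 14% unhealed at Day 10.
- Restricted mean to Day 10: (8.5 − 2²/14) − (7.5 − 1²/14) = 8.21 − 7.43 = 0.79.
- Unhealed left out: 7.5 − 7.0 = 0.5.
- Closed at Day 7: (8.5 − 5²/14) − (7.5 − 4²/14) = 6.71 − 6.36 = 0.36.

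Only 29% and 43% heal by Day 7 in this case, against Section 3, so it is a bound and not an expectation.

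**5. Direction when unhealed episodes are left out.** Comparator: half heal at Day 6, half at Day 10. EED: half at Day 2, half at Day 10. Means 8 and 6, difference 2. Dropping those unhealed at Day 7 gives 6 − 2 = 4. The bias need not be toward zero.

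**6. Power, simulated, 10 per arm, 1-day effect, exact dates (t-test closed at 7 v to Day 10).**
- Uniform 4–9 v 3–8: 23% v 29% (6 points).
- Uniform 5–12 v 4–11: 13% v 15% (2 points).
- Lognormal: 40% v 44% and 19% v 23% (about 4 to 5 points).

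**7. The proposed contrast.** The restricted-mean difference to Day 10 has power 29% where the t-test to Day 10 has 29% (4–9 v 3–8, nobody censored), and 48% v 49% (5–12 v 3–10, some censored). With exact dates its null rejection is 4.9% and 4.5%. The 95% interval has a half-width of about 1.3 to 1.8 days.

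**The case against.** The strongest reply is that the documents already define duration to healing, that few lesions should be unhealed at Day 10, and that this is a pilot whose estimates will be imprecise under any rule. Most of that stands and limits the point. It does not supply a value for a subject who attends every visit and is still unhealed at Day 10, nor a contrast for the Kaplan-Meier curves.

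Four stronger readings are tempting and not supported:
- *A reader might infer that Section 7.1 cuts every episode at 7 days.* It names that date as a reference for the photograph review, then defines duration from prodrome to healed and asks for all the information gathered.
- *A reader might infer a large loss of power.* If healing is read only at scheduled visits, a 2-day effect (4–9 v 2–7) gives 54% v 83%, a 29-point loss. That model moves all healing after Day 7 to Day 10, whereas Section 3 holds EOS as soon as the lesion heals and Section 7.1 uses a diary date. It also inflates the true 2.0 days to 2.4.
- *A reader might infer that early leavers distort the result.* Section 6.2 foresees them ("If at any time during the study, a subject wants to stop participating"), but the Per Protocol population in Section 9.1 requires attendance at all visits. Section 9.2 does not name its population, but Per Protocol is the only one defined besides Safety.
- *A reader might infer that dropping unhealed episodes always shrinks the difference.* Step 5 shows otherwise.

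**Conclusion.** The point holds as a mismatch between method and data: the only between-arm test named for duration cannot use an episode the protocol expects may occur, and the method that can has no contrast. The 7-day reference is a stray inconsistency. The impact is confined to secondary endpoints.

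If the 7-day date were used, a 1-day difference would become about 0.5 to 0.7 day under the healing times in steps 2 and 3 (0.36 in the harsher case). With follow-up used to Day 10 the loss is small in those settings. For a 1-day effect with exact dates the power change is about 2 to 6 points, so the harm is mainly to the estimate. All sizes rest on assumed distributions. The textual findings do not. The change is worth making because it is cheap, not because the trial's main result is at risk.

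**What to change.** **Section 7.1.** State that, for measuring duration, the end date is the observed healing date through EOS/Day 10, and that the 7-day treatment date does not end the episode. Keep completion of treatment as the reference for the primary endpoint.

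**Section 9.2.** For prodrome-to-healed duration (clock from Day 1, common horizon Day 10), make the between-arm comparison the Kaplan-Meier restricted-mean difference to Day 10 with a 95% confidence interval. Censor unhealed episodes at Day 10, or at the last assessment if earlier. Use this in place of the t-test for duration whether or not any episode is censored, so that the method does not depend on the data. A log-rank test would also be acceptable; its simulated null rejection at 10 per arm was 6.3% to 6.4%, slightly above 5%.

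**Stage 3-to-healed duration (synopsis).** Use the same censoring, with a horizon that all subjects can reach. A lesion first at Stage 3 on Day 3 has only 10 − 3 = 7 days of follow-up, so Day 10 is not a common horizon on that clock.

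**Cost.** Wording only; no new visits or data. There is slightly more analysis work, and the result reads as mean days to healing within the first 10 days.

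Separately, Section 1.1 gives a 7-day treatment maximum while Section 3 and the synopsis allow up to 10 days. The sponsor must reconcile these passages; no view is taken here on which is right.

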9.3 Safety Analysis

The safety analysis will be conducted on the Safety population.

Collection of AEs will begin on the first day of treatment and will be reported in simple per-subject listings.

10. SCHEDULE OF ASSESSMENTS

ASSESSMENT	SCREENING	Induction Visit	Daily after induction visit to Day 1	DAY 1	DAY 5	DAY 7	DAY 10/ EOS	Follow -up phone call (EOS +2 days)
Informed Consent	X							
Medical/HSV History	X	X (med hx only)						
Urine Pregnancy Test (for woman of child bearing potential only)	X							
Limited Physical Exam	X	X						
Concomitant Medications	X	X						X
UV susceptibility test / MED testing	X (exposure)							
MED Reading		X						
Randomization		X						
UV exposure at 3 x MED (cold sore inducing)		X						
Study Product Dispensed		X						
Dosing Begins				X				
Dosing Ends						X		
Collect Study Product (including empty tubes/bottles)							X	
Photograph of irradiated area and lesion may be taken		X		X	X	X	X	X
Measurement of lesion (if possible)				X	X	X	X	X
Dispensing of Diary Card		X						
Review of Diary Card/Dosing compliance				X	X	X	X	
Solicitation of Adverse Events			X	X	X	X	X	X
Rating of lesion by blinded assessor				X	X	X	X	
Phone call to check for prodromal senses			X
